NCT Number: NCT04986072

Official Title: Sodium Nitroprusside in Early Course Schizophrenia

Document Type: Study Protocol and SAP

Document Date: 07/17/2023

PART B STUDY DESCRIPTION

Title of Protocol	Proof of Mechanism Study using a Retinal Biomarker to Predict Treatment Response with Intravenous Sodium Nitroprusside in Symptomatic Early Course Schizophrenia
Principal Investigator	[name]

B1. PURPOSE OF PROTOCOL

- 1. The main purpose of this proposal is to determine the effectiveness of a single intravenous administration of sodium nitroprusside (SNP) (0.5 mcg/kg/min for 4 hours) on positive and negative symptoms in symptomatic Early Course Schizophrenia (ECS).
- 2. To examine the effect of SNP on cognition and retinal imaging phenotypes in ECS, and whether baseline retinal microvasculature or inflammation (CRP levels) correlate with a change in psychosis symptoms or cognition.

We hypothesize that SNP will improve psychosis symptoms and cognition in symptomatic ECS and that this change can be predicted by retinal vessel morphology or CRP levels. We predict that SNP will improve oxygen supply and reduce inflammation, which will be evidenced by reductions in retinal vessel phenotypes.

B2. SIGNIFICANCE AND BACKGROUND FOR THE STUDY

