Nitric oxide (NO) signaling is a potential mechanism for protecting the microvasculature against oxidative stress, inflammation and endothelial dysfunction¹⁶. NO-donors (NOD) can protect nerve tissue from injury and preserve the integrity of the blood brain barrier, suggesting that cerebral vascular endothelium is essential in the control of vascular inflammatory and oxidative responses, leukocyte migration, and the production of inflammatory mediators¹. In addition to reducing oxidative stress and inflammation, NOD can increase cerebral and retinal blood flow¹⁶. In healthy volunteers, SNP dose dependently increases retinal arteriolar/venular diameter, and leukocyte flow¹⁷. However, in pathologic states such as ischemia, SNP can enhance neuroprotection by increasing arteriolar diameter and reducing venular leukocyte adhesion (i.e., reduced venular diameter), which together facilitate blood flow¹⁶. Preclinical and clinical evidence have shown that SNP may have an antipsychotic profile. In preclinical studies, SNP has been used to prevent SZrelated behaviors in a spontaneously hypertensive rat model¹⁸. Five clinical studies to date have examined the effects of SNP on psychosis symptom improvement with mixed results. In one study, a single infusion of SNP resulted in an immediate improvement in overall psychosis and negative symptoms in an antipsychotic medicated ECS group with <5 years illness duration, an effect that persisted for 4 weeks¹⁹. However, four studies performed in chronic SZ did not find any evidence of symptomatic improvements, with two of these studies providing repeated infusions of SNP^{20–23}. There were several limitations with these negative studies: older patient population, longer durations of illness (8-17 years), and the absence of a treatment biomarkers. These studies neglected to consider an alternative mechanism of action for SNP, which would include the protection against inflammatory mediated microvascular dysfunction. Another important factor to consider is that while ~70 randomized control trials to date have examined adjunctive antiinflammatory drugs on psychosis symptoms or cognition in SZ²⁴, six of these have performed post hoc analyses of participants with elevated levels of individual inflammatory markers (such as CRP), and their findings strongly suggest that ECS individuals with elevated peripheral inflammation have the greatest benefit with anti-inflammatory drugs²⁴. Thus, it is conceivable that treatment effects could be stronger in participants with elevated markers of inflammation or disruptions in related pathways. As a result, in order to SNP to be effective it should be administered to patients with ECS. Thus, further work is needed to determine whether the effect of SNP treatment is dependent on a patient's illness duration and whether a retinal biomarker for microvascular dysfunction/inflammation can predict treatment response to SNP. There is a growing literature on how increased peripheral inflammation and

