
microvascular dysfunction are central to the pathophysiology of SZ. Advances in retinal imaging

now allow for the accurate quantitative assessment of the condition of retinal microvessels, and early studies implicate microvascular dysfunction in SZ, but the specific pathophysiological mechanisms underlying greater length, density, capillary network, and diameter are not yet entirely understood. A potential target is NO signaling, which is involved in vessel protection from oxidative stress, inflammation and endothelial dysfunction, and treatment with NOD have been shown to reduce oxidative stress/inflammation and to increase cerebral blood flow in cerebrovascular disorders. Anti-inflammatory drug trials in SZ suggest that ECS individuals with elevated peripheral inflammation show the greatest benefit to adjunctive anti-inflammatory treatments. Also, there is a growing interest in the use of SNP in SZ and studies to date have been mixed. Hallak et al (2013) demonstrated that a single infusion of SNP in patients with ECS was both safe and associated with immediate and longer-term clinical outcome. While three other studies demonstrated that SNP was well-tolerated in patient with multi-episode SZ, they were not able to replicate Hallak's finding, which was likely due to the disease heterogeneity, the inclusion of an older population with a longer duration or multi-episodes of illness, and the lack of treatment biomarkers. Thus, the principal goal in the field of SZ is to identify biomarker-based targets for early intervention, evidence of engaging this target by selective interventions and assessing therapeutic efficacy²⁵.

References:

- 1. Abbott, N. J. Anatomy and Physiology of the Blood–Brain Barriers. in *Drug Delivery to the Brain* (eds. Hammarlund-Udenaes, M., de Lange, E. C. M. & Thorne, R. G.) vol. 10 3–21 (Springer New York, 2014).
- 3. [name], P. *et al.* Multivariate relationships between peripheral inflammatory marker subtypes and cognitive and brain structural measures in psychosis. *Mol. Psychiatry* (2020) doi:10.1038/s41380-020-00914-0.

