Baseline demographic details will be compared between the SNP and placebo groups using independent-samples t tests or Mann-Whitney U tests where appropriate using R software. Categorical data will be compared using chi-square tests. Effect sizes will be provided using Cohen's d. The primary outcome (PANSS) will be analyzed using a 2 (treatment group) × 5 (time point) mixed analysis of variance (ANOVA). Analyses of secondary outcome measures will be compared using a 2-group x 4 time point mixed ANOVA for cognition and a 2 x 2 for retinal measures. The relationship between baseline or change in retinal vessel measures or CRP and change in PANSS scores or cognition will be performed using Pearson's (parametric) or Spearman's (non-parametric) correlation.

C. Subject Selection

Population: Men and women, 18-60 years of age, from diverse background, symptomatic, with early course schizophrenia, and meet all study inclusion and exclusion criteria.

Inclusion criteria for ECS patients are: a DSM-V diagnosis of SZ or schizoaffective disorder with ≤5 years from the onset of psychosis and up to 2 years of lifetime exposure to antipsychotics, total score of ≥55 on the PANSS with a score of ≥3 on 1 or more PANSS Positive Scale items (delusions, conceptual disorganization, hallucinatory behavior, suspiciousness, or unusual thought content) and/or score of ≥3 on the CGI-S scale, taking antipsychotic for 8 weeks with a stable dose of 4 weeks (no medication change will be allowed during the trial), English proficiency, understands and is able, competent and willing to give informed consent in accordance with the International Conference on Harmonization Good Clinical Practice Guidelines.

Exclusion criteria are:

- Presence of renal, hepatic, cardiac, hematologic, neurologic impairments or abnormal physical exam.
- Presence of retinal disease (myopia >4.0 diopters)

- Baseline systolic BP <100mmHg or symptomatic orthostatic hypotension (systolic BP <90 mmHg or diastolic BP <60 mmHg) with any of the following: lightheaded or dizzy, blurry vision, weakness, syncope, confusion, nausea.
- Pregnant or breastfeeding (pregnancy test at screening visit and prior to randomization).
- Abnormal laboratory testing (see appendix)
- Treatment with medications that may interfere with the metabolism or excretion of SNP or are associated with drug-drug interactions (see list of medications below).
- Prior history of intolerance to SNP
- Currently taking clozapine or chlorpromazine

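### The biomarker–response analysis is an unadjusted correlation across ages 18–60; an age-adjusted coefficient should be pre-specified beside it, because part of a raw correlation could reflect age

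*Combined protocol and SAP*

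**What the plan says.** The hypothesis in section B1 is that SNP improves symptoms and cognition and that "this change can be predicted by retinal vessel morphology or CRP levels". The Outcome paragraph of B3.A makes the relationship between baseline or change in retinal measures or CRP and change in symptoms and cognition a secondary outcome, to be examined against placebo.

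The only analysis given is in B3.B: "change in PANSS scores or cognition will be performed using Pearson's (parametric) or Spearman's (non-parametric) correlation". It names no covariate, partial correlation, regression, age stratum or treatment-by-biomarker term. It does not say whether one arm or both are used.

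On eligibility, B3.C admits "Men and women, 18-60 years of age, from diverse background, symptomatic, with early course schizophrenia" and requires "≤5 years from the onset of psychosis and up to 2 years of lifetime exposure to antipsychotics". These limits cap illness duration and drug exposure, not age. Randomization (B3.A, Study Design) takes account of gender and race; age is not named.

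Section B2 explains the earlier negative trials twice. The first list is "older patient population, longer durations of illness (8-17 years), and the absence of a treatment biomarkers". The second says of the failure to replicate: "which was likely due to the disease heterogeneity, the inclusion of an older population with a longer duration or multi-episodes of illness", followed by the lack of treatment biomarkers.

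**The concern.** The authors count older age among the possible reasons for non-response, restrict illness duration, and leave age open over 42 years (60 − 18). If a retinal measure or CRP also changes with age, age sits behind both sides of the planned correlation. A single Pearson or Spearman coefficient cannot then separate a microvascular or inflammatory signal from age.

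The study title promises a retinal biomarker that predicts response. Age is known without a scan, so a marker that only tracks age would add nothing in practice, and the planned analysis would not reveal this. The reverse can also happen: if age acts against the marker, a raw coefficient understates a real association.

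Randomization and the planned between-arm comparison of baseline demographics do not help, because the correlation compares participants by marker level rather than by assigned arm.

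**Working it through.** **Plan's own figure.** The documents give no power or sample-size figure for the correlation. The stated power for a 10-point PANSS difference (SD 6, 16 per arm, two-sided 0.05) is met: the exact t calculation gives 99.5% against the stated >80%. It concerns the group comparison and does not bear on this point.

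**Inputs from the documents.** 16 participants per arm, 32 in total; two-sided alpha 0.05 (B3.B, Power calculation).

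**Assumed inputs, shown as a range.** The correlation of age with marker, *a*, and of age with response, *b*. Neither is in the documents.

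**Induced correlation.** If the marker has no effect of its own, expected raw r = *a* × *b*:
- 0.3 × 0.3 = 0.09
- 0.4 × 0.4 = 0.16
- 0.5 × 0.5 = 0.25

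With both arms pooled and the age–response link in the SNP arm only, half the participants carry the association, so expected r is about *ab*/2: 0.045, 0.08 and 0.125.

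**Rejection rates.** Simulated with 40,000 normal samples per setting, raw Pearson test at 5%:

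| *a* and *b* | SNP arm only, n=16 | Pooled n=32, link in SNP arm only | Pooled n=32, link in both arms |
|---|---|---|---|
| 0.3 | 6% | 5.5% | 8% |
| 0.4 | 9% | 7% | 14% |
| 0.5 | 15% | 11% | 28% |

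In the middle column, adding the planning difference between arms (10/6 = 1.67 SD) lowers the rates to about 5.5%, 6.4% and 8.2%. If age is unrelated to the marker, the rate stays at about 5%.

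**After adjustment.** The partial correlation given age is

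r(MY·A) = (r(MY) − r(MA) r(YA)) / √[(1 − r(MA)²)(1 − r(YA)²)], with n − 3 degrees of freedom,

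where M is the marker, Y the response and A age. It rejects in about 5% in every setting above.

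**Cost: degree of freedom.** The critical |r| moves from 0.497 to 0.514 at n=16 and from 0.349 to 0.355 at n=32.

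**Cost: shared signal.** Suppose the marker truly drives response (r = 0.5) and age acts only through it. The true partial correlation is then smaller:
- age–marker 0.4: (0.5 − 0.4 × 0.2) / √(0.84 × 0.96) = 0.468
- age–marker 0.5: (0.5 − 0.5 × 0.25) / √(0.75 × 0.9375) = 0.447

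Power falls from about 53% to 44% and 40% respectively at n=16, and from about 85% to 78% and 73% at n=32.

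**Masking.** With standardized effects of 0.5 for the marker and −0.4 for age, and age–marker correlation 0.4, the expected raw r is 0.5 − 0.4 × 0.4 = 0.34. The raw test detects the marker in about 25% (n=16) or 49% (n=32) of samples, against 44% and 78% after adjustment.

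**The case against.** Confounding needs two links, and the documents supply at most one. Nothing in them relates age to retinal measures or CRP. The other link is the authors' conjecture about earlier trials, not a measurement. It names age together with longer or multi-episode illness, heterogeneity and missing biomarkers, and B2 goes on to ask whether the effect depends on illness duration, which the eligibility criteria already restrict. A reader might infer that, on the protocol's own reasoning, age predicts response among early-course patients; the documents do not say that. This objection stands: the result is a possible bias of unknown size.

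A reader might also take 8%, 14% and 28% as the error rates for the full sample of 32. Those figures require age to predict change on placebo as well, whereas B2 speaks only of response to SNP. The rates consistent with that premise are the lower ones.

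It can further be said that a raw correlation answers an exploratory question, that incremental value over age is a stricter claim than the protocol makes, and that smoking, BMI or baseline severity could be argued in the same way. This has some force and argues against replacing the raw coefficient. It does not argue against adding an adjusted one: age is the factor that B2 itself raises, and the eligibility criteria leave it wide.

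Finally, age adjustment does not reach the larger gap. B3.A asks for a comparison with placebo, but B3.B plans no treatment-by-biomarker comparison. That is correct, and the claim made for the adjusted result has to be limited accordingly.

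**Conclusion.** The point holds in a limited form. B3.B offers no way to tell whether a marker–response correlation merely reflects age, although B2 lists older age among the likely reasons for earlier non-response and eligibility spans 18 to 60. If both age links lie between 0.3 and 0.5, the false-positive rate rises from 5% to about 6–15% in the SNP arm, or to about 5.5–11% with the arms pooled and the link confined to SNP. It remains at 5% if either link is absent. All of this rests on an assumed age–marker association and on normal, linear relationships.

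It would go too far to conclude that the planned correlation is invalid or should be dropped. Adjustment can remove true signal, so neither coefficient suffices alone. It would equally go too far to read a significant age-adjusted coefficient as evidence of predicting response to SNP. For a secondary analysis in a 32-person pilot, this is a worthwhile refinement rather than a serious flaw.

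**What to change.** Add to B3.B that each biomarker–response correlation will be reported both raw and adjusted for age, the latter as a partial correlation (rank-based where Spearman is used) or as a regression of PANSS or cognition change on the marker with age as a covariate. State that a marker will not be described as predicting response beyond age unless the age-adjusted estimate supports it. State which arm or arms enter the analysis.

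Also state that neither coefficient by itself shows prediction of response to SNP. That needs a treatment-by-biomarker comparison and, if age may modify response, a treatment-by-age term in the same model.

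The cost is a few sentences in the plan; age is already recorded. Statistically it is one degree of freedom, plus the loss of power shown above when marker and age are correlated. That loss should be disclosed, and it is the reason for reporting both estimates.

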Laboratory Procedures: Screening blood work will be fasting, and blood work taken as part of the study treatment monitoring process will be non-fasting as a precautionary measure to reduce the risk of a hypotensive episode.

Routine laboratory panels will include (see Section C below for exclusionary laboratory criteria):

- Hematology (absolute and percentage): White blood cell (WBC) count with differential (absolute neutrophil count, lymphocytes, monocytes, basophils, and eosinophils), red blood cell (RBC) count, hemoglobin (Hgb), hematocrit (Hct), and platelet count.
- Comprehensive Metabolic Panel: Glucose, sodium, potassium, calcium, chloride, carbon dioxide, blood urea nitrogen (BUN), creatinine, calculated glomerular filtration rate, uric acid, phosphorus, magnesium, total protein, albumin, lipid panel (triglycerides, total cholesterol, HDL-cholesterol, calculated LDL-cholesterol) aspartate amino transferase (AST), alanine amino transferase (ALT), alkaline phosphatase (ALP), gamma glutamyl transpeptidase (GGT), total bilirubin, creatine phosphokinase (CPK), creatine kinase (CK) thyroid stimulating hormone (TSH) and uric Acid, and C-Reactive Protein (CRP).
- Serum Pregnancy: Serum beta human chorionic gonadotropin (Beta- hCG).
- Urinalysis: color, appearance, specific gravity, pH, ketones, protein, glucose, nitrite, leukocyte esterase, and occult blood; microscopic examination of sediment will be performed only if the results of the urinalysis evaluation are positive (microscopic examination may include but is not limited to WBC count, red blood cell (RBC) count, casts, and crystals).
- Urine drug screen: cannabis, opioids, cocaine, amphetamines, methadone, cannabinoids, barbiturates, benzodiazepines, methamphetamine, and phencyclidine.
- Urine Pregnancy Test: urine pregnancy test will be performed in female subjects of childbearing potential using a dipstick urine test.

12-Lead Electrocardiogram (ECG): A 12-lead ECG will be taken at following a supine rest for 5 minutes. ECG parameters including the QT interval, Bazett's corrected QT interval (QTcB), and QTcF Fridericia's corrected QT interval (QTcF), pulse rate (PR), and QRS intervals, and heart rate will be recorded. The ECGs will be reviewed by the Co-I to assess any immediate abnormalities.

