undergo training by critical care nursing to be able to safely administer nitroprusside in the CRC. The CRC is equipped with an Omnicell and can be stocked with rescue medications needed for the study. The CRC has the capability to conduct continuous monitoring of heart rate, blood pressure, pulse oximetry and telemetry (see attached support letter from the CRC).

The CRC and the PI and co-investigators are prepared to ensure that this study protocol is conducted safely outside of an ICU setting, and an outline of the protocol, including procedures for study drug administration and monitoring, is as follows:

Patient Selection

Medically Relevant Exclusion Criteria:

- Presence of renal, hepatic, cardiac, hematologic, neurologic (seizures or elevated intracranial pressure) impairments.
- Pregnant or breastfeeding. Women of childbearing potential must have a negative pregnancy test performed at the screening visit prior to the baseline assessment and randomization.
- Physical exam suggestive of an underlying disease state that may, in the opinion of the investigators, confound the results of study, increase risk to the subject or lead to difficulty complying with the protocol.
- Baseline systolic BP <100mmHg or symptomatic orthostatic hypotension (systolic BP <90 mmHg or diastolic BP <60 mmHg with any of the following: lightheaded or dizzy, blurry vision, weakness, syncope, confusion, nausea).
- Abnormal laboratory testing (see appendix)
- Medications that interfere with the metabolism or excretion of nitroprusside or are associated with drug-drug interactions (see appendix below)
- Medications that could pose a significant risk to the participants' health
- Hypersensitivity to SNP
- Currently taking clozapine or chlorpromazine
- Subjects with a current (within the last 3 months) DSM-V diagnosis of alcohol or substance use disorder or dependence (excluding nicotine) at the screening visit
- Has tested positive for any of the following: cannabis, opioids, cocaine, amphetamines, barbiturates methadone, methamphetamine and phencyclidine at the screening or baseline visits.
- Subjects at imminent risk of suicide or injury to self or others or history of significant suicide attempt within the last 12 months.

Screening Pre-infusion Visit

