- Treatment with anti-inflammatory drugs, hormones or immunosuppressant agents in the 6 months before study entry
- Subjects with a current DSM-V diagnosis of alcohol or substance use disorder or dependence (excluding nicotine)
- Urine drug screen tested positive for any of the following: cannabis, opioids, cocaine, amphetamines, barbiturates methadone, methamphetamine and phencyclidine at the screening or baseline visits
- Subjects at imminent risk of suicide or injury to self or others or history of significant suicide attempt within the last 12 months as measured by the C-SSRS together with the opinion of the trial investigator.
- Subjects that have taken an investigational drug or taken part in a clinical trial within 30 days prior to screening.
- Participation for any reason would compromise patient safety or integrity of the study in the opinion of the investigator.

Exclusionary Safety Values of Potential Clinical Concern

Complete Blood Counts	
Leukocytes	<2 or >17.5 x 10 ³ /mm ³
Platelets	<75 or >700 x 10 ³ /mm ³

Comprehensive Metabolic Panel	
Sodium	<1.1 times the lower limit or >1.1 times
	upper limit of the reference range
Potassium	<1.1 times the lower limit or >1.1 times
	upper limit of the reference range
Chloride	<1.1 times the lower limit or >1.1 times
	upper limit of the reference range
Glucose	>2 times the limits of the reference range
Blood Urea Nitrogen (BUN)	>1.3 times upper limit of the reference range
Creatinine	>1.3 times upper limit of the reference range
Calculated Glomerular Filtration	<60
Total bilirubin	>2 times the upper limit of the reference
	range
Aspartate amino transferase (AST)	>3 times upper limit of the reference range
Alanine amino transferase (ALT)	>3 times upper limit of the reference range

Alkaline phosphatase (ALP)	>3 times upper limit of the reference range	
Creatine phosphokinase (CPK)	>3 times upper limit of the reference range	
Creatine kinase (CK)	>3 times upper limit of the reference range	
Thyroid Stimulating Hormone (TSH)	>3 times upper limit of the reference range	
Uric acid	>3 times upper limit of the reference range	
Lipid panel (triglycerides, total cholesterol (C), HDL-C, calculated LDL-C)	>3 times the upper limit of the reference range	
Serum beta human chorionic gonadotropin (Beta- hCG)	< 6 IU/L negative	

Drug-Drug Interactions:

-Risk X: Avoid combination Bromperidol Phosphodiesterase 5 Inhibitors Riociguat

-Risk D: Consider therapy modification Amifostine Obinutuzumab

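### The low-side exclusion bound for sodium, potassium and chloride (1.1 times the lower limit) lies inside the normal range and excludes normal values

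*Combined protocol and SAP*

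**What the plan says.** B3 section C (Subject Selection) contains a table headed "Exclusionary Safety Values of Potential Clinical Concern". Its sodium, potassium and chloride rows carry the same entry: a value is exclusionary if it is "<1.1 times the lower limit or >1.1 times" the "upper limit of the reference range".

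The table is the operative one. Laboratory Procedures in B3 section A directs the reader to it ("see Section C below for exclusionary laboratory criteria"). It gives content to the criterion "Abnormal laboratory testing (see appendix"), which stands both in the medically relevant exclusions of the infusion protocol and in the exclusion list of section C. The three electrolytes are in the study panel ("Comprehensive Metabolic Panel: Glucose, sodium, potassium, calcium, chloride, carbon dioxide"). The population statement in section C requires participants to satisfy every inclusion and exclusion criterion, so the table is binding.

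**The concern.** A safety exclusion of this kind normally allows a margin outside the reference range before a patient is turned away. The high side does so: the value must exceed the upper limit by more than 10%. On the low side the same factor of 1.1 moves the threshold up, into the normal range, so patients with normal results are excluded under a criterion meant for abnormal ones.

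This governs entry to a vasodilator infusion given outside an ICU, in a single-centre trial of 32 patients. Read literally, the rule bars patients with normal results, and under some reference ranges it bars all of them. If staff set it aside, each such enrolment departs from the written criteria. The table then holds no valid low threshold, and the decision falls to case-by-case medical clearance.

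**Working it through.** **Inputs.** From the table: low-side multiplier 1.1 on the lower limit L, and high-side multiplier 1.1 on the upper limit U. The document gives no reference limits, so every range below is an assumption (mmol/L).

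**Direction.** For any L > 0, 1.1 × L − L = 0.1 × L > 0. The bound is therefore always above the lower limit, and values from L up to 1.1 × L are normal but excluded. This step needs no outside figure.

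**Size.** Share of the width of the normal range excluded = min(1, 0.1 × L / (U − L)). The whole range is excluded when U/L < 1.1.

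| Analyte | Assumed range | Bound 1.1 × L | 0.1 × L / (U − L) | Share excluded |
|---|---|---|---|---|
| Sodium | 135–145 | 148.5 | 13.5/10 | 100% |
| Sodium | 133–145 | 146.3 | 13.3/12 | 100% |
| Sodium | 133–147 | 146.3 | 13.3/14 | 95% |
| Sodium | 132–148 | 145.2 | 13.2/16 | 83% |
| Sodium | 130–150 | 143.0 | 13.0/20 | 65% |
| Chloride | 98–107 | 107.8 | 9.8/9 | 100% |
| Chloride | 96–106 | 105.6 | 9.6/10 | 96% |
| Chloride | 96–108 | 105.6 | 9.6/12 | 80% |
| Chloride | 95–110 | 104.5 | 9.5/15 | 63% |
| Potassium | 3.6–5.0 | 3.96 | 0.36/1.4 | 26% |
| Potassium | 3.5–5.0 | 3.85 | 0.35/1.5 | 23% |
| Potassium | 3.3–5.1 | 3.63 | 0.33/1.8 | 18% |
| Potassium | 3.3–5.3 | 3.63 | 0.33/2.0 | 17% |

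With sodium 135–145 the literal eligible window runs from 148.5 to 1.1 × 145 = 159.5, so the row admits only patients whose sodium is above normal. The shares are of range width, not of patients. Where the share is 100%, though, every patient with a normal value is excluded however values are distributed.

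**Consistency within the table.** Every multiple of an upper limit in the table (1.1, 1.3, 2 or 3 times) puts the threshold outside normal. Only these three low-side bounds fall inside it. Identical wording in three rows makes a PDF reading fault unlikely, and nothing elsewhere in the document restates or corrects the bound.

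**What might have been meant.** Candidate low bounds, with assumed lower limits of 135, 3.5 and 98:

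| Reading | Sodium | Potassium | Chloride |
|---|---|---|---|
| 0.9 × L | 121.5 | 3.15 | 88.2 |
| L / 1.1 | 122.7 | 3.18 | 89.1 |
| 0.95 × L | 128.3 | 3.33 | 93.1 |
| L itself | 135 | 3.5 | 98 |

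**The case against.** The strongest reply is that this is an evident slip that no clinician would apply literally. The governing criterion speaks of abnormal results and the table heading of clinical concern, and a sodium within the reference range is neither. The table is loosely drafted elsewhere too: its beta-hCG row prints the negative range, which taken literally as exclusionary would rule out every non-pregnant woman. The error is conservative, because low values remain excluded. Other safeguards exist as well: medical clearance overseen by the critical-care co-investigator, renal and cardiac exclusions, ECG and vital-sign monitoring, and the investigator's discretion to exclude. The two natural readings, 0.9 × L and L/1.1, differ by only about 1%. Nothing in the document shows that enrolment was blocked or deviations recorded.

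Much of this stands. The literal bound can be computed, so the trouble is that it is wrong, not that it is undefined. The safety consequence is narrow, and how staff have applied the rule is unknown. Three points remain:

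- Sensible reading by staff still leaves enrolments in breach of a binding criterion. The investigator-discretion clause only adds exclusions; it does not waive a listed one.
- The beta-hCG row labels its value as negative and so explains itself. The electrolyte rows contain nothing comparable.
- The intended limit is not stated. The two closest readings nearly agree, but nothing in the text rules out a tighter bound, and a sodium limit of 121.5 is a different clinical decision from 128.3 or 135.

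**Conclusion.** The concern holds. The low-side bound for sodium, potassium and chloride is a wrong threshold in a binding eligibility rule and should be corrected. That it excludes normal values follows from the stated multiplier alone, whatever the laboratory's reference range.

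The extent depends on assumed ranges. As shares of the width of the normal range, it is 95–100% for sodium with the narrower ranges tried (65% at the widest), 63–100% for chloride and about 17–26% for potassium. Under a sodium range such as 135–145, the rule read literally would stop nearly all enrolment or turn most enrolments into eligibility deviations. It would not admit patients with low electrolytes.

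**What to change.** Amend the low side of the three rows to a multiplier below 1, or to explicit absolute limits, and have the investigator and the critical-care co-investigator confirm the values. Mirroring the high side gives 0.9 × L, the first line of the table of candidate bounds above. That sodium limit is permissive, so a tighter one such as 0.95 × L may be preferred; the choice is clinical and the document does not settle it. The high-side margin is equally wide and can be confirmed at the same time.

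Then check everyone already screened against the corrected rule and document the result. The cost is a three-cell correction in a protocol amendment plus a review of the screening log.
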